7.3 Reporting of SAEs by investigator

All SAEs must be reported by the investigator within 24 hours after the SAE becomes known using the 'Serious Adverse Event' form to the Data Management. The initial report must be as complete as possible including details of the current illness and (serious) adverse event and an assessment of the causal relationship between the event and the trial procedures.

7.4 Reporting of OEs by the investigator

All Outcome-events must be reported by the investigator within 24 hours after the OE becomes known using the 'Outcome Event' form to the Data Management. The initial report must be as complete as possible including details of type of stroke (ischemic vs. hemorrhagic, territory of stroke, and severity of stroke). 30 days after symptom onset the modified Rankin Score patient has to be assessed and to be transferred to the Data management using the 'Outcome Event' form. All OEs are also evaluated by the EEC.

7.5 Expedited reporting

SAEs, and OEs resulting in death or being life-threatening will be reported to the ethics committee (EC) according to EC standing rules and to all participating investigators.

8 DATA MANAGEMENT

8.1 Data collection

All findings including clinical and laboratory data will be documented in the subject's medical record and in the electronic CRF. The electronic CRF has a series of inbuilt validation routines and plausibility checks. The investigator will be immediately informed if the data entered does not comply with the data validation rules. The fully entered parts of the CRF will be mailed as encoded PDF-Files to the main investigator of the specific site. The PDF can be printed and support monitoring activities at the study site. A second check will be performed by the data management which triggers the query process. Queries will be sent directly to the investigator and a copy to the monitor. The investigator is responsible for ensuring that all sections of the CRF are completed correctly and that entries can be verified against source data.

8.2 Data handling

Data handling is described in detail in the Data Management Plan and the Data Validation Plan.

Each study site will have secured internet access to the electronic study data base. The data will be entered directly to the database. During entering a series of data check will be run automatically and the person entering the data will be reminded immediately if there are specific errors or inconsistencies. These data checks will be formulated in the data validation plan. After finishing specific parts of the eCRF the study site will get a PDF with the patient data via an encoded email.

A more thorough data check will be performed by the data management. This second view generates the queries which are sent to the study site as well as to the monitor.

A responsible investigator will be obliged either to correct the implausible data or to confirm its authenticity and to give appropriate explanation. If not corrected, the data will be flagged, rendering a check of all questionable entries conveniently possible. A responsible monitor will check all flagged data and will generate questions, which will be

sent back to the responsible investigator. The investigator will have to resolve all 'discrepancies'.

Further checks for plausibility, consistency, and completeness of the data will be performed after completion of the study. Queries will be generated on the basis of these checks combined with a visual control by a responsible monitor/data manager.]

All missing data or inconsistencies will be reported back to the center(s) and clarified by the responsible investigator. If no further corrections are to be made in the database it will be declared closed and used for statistical analysis.

All data management activities will be done according to the current Standard Operating Procedures (SOPs) of the IBE.

8.3 Storage and archiving of data

All important trial documents (e.g. Investigator Site File, subject identification log, CRF) will be archived for at least 10 years after the end of the trial.

9 DATA ANALYSIS / STATISTICAL METHODS

9.1 Sample size calculation

Sample size calculations were performed for the efficacy endpoints.

OLD: Since a hierarchical testing procedure is used, a 5% significance level for each step of the procedure can be chosen. The first level consists of two simultaneously performed tests. In order to assure an overall level of 5% for this step, the closed testing procedure is used and the two comparisons CAS versus BMT and CEA versus BMT are performed as two-sided tests with $\alpha=2.5\%$. The event rate of CAS (as well as CEA) is assumed to be 6.4% (combining short-term and 5-year event rates). The BMT event rate is set to 11.8%. The sample size in the CAS (CEA) arm is twice the number of patients in the BMT arm. The power of each comparison is set to 90%. We need a high chance to show simultaneously superiority for CEA as well as CAS in comparison with BMT in order to clinically interpret the non-inferiority aimed at the second step of the procedure. The comparison needs 1,080 patients in the CAS and the CEA and 540 patients in the BMT arm when a two group continuity corrected chi-square test is used. For this scenario (1,080/1,080), a two-sided significance level of $\alpha=5\%$, and a non-inferiority margin of 2.5% implies for the non-inferiority assessment between CAS and CEA a power of 66%. A power of 80% for the non-inferiority test is reached with a sample size of 1,505 patients in each group (CAS/CEA).

The CAS/BMT as well as the CEA/BMT comparison (SPACE-2a) will be performed on an ITT population. In contrast the CAS/CEA non-inferiority assessment (SPACE-2b) will be based on an ITT as well as on a PP population [11]. The PP analysis for non-inferiority needs a group size of 1,505 patients. In SPACE 3% of the patients switched between treatment modalities or were not treated. A recruitment of 1,550 patients into the CEA and CAS groups is needed to correct for such a deviation from the allocated treatment and to allow a sufficient PP-analysis. This increases the power of the comparisons CAS/BMT and CEA/BMT to 93%.

Therefore, the total size of the trial is chosen as $(1,550+1,550+540=)$ **3,640** patients.

NEW: The event rate in the BMT-group is expected as 0.01 per year, a hazard ratio with any type of intervention is set as 0.50 leading to an average risk of 0.005 per year including the periprocedural risk for both types of intervention. In case of a design without interim analysis 1,624 patients in total are needed to show the assumed difference on a two- sided significance level of 5% and with a power of 80% assuming an accrual time of 3 years and a follow-up time of 5 years.

Planning one interim analysis in a group sequential design after five years, a total of 1,636 patients is needed to show the assumed difference on a two- sided significance level of 5% and with a power of 80% assuming an accrual time of 5 years and a follow-up time of 3 years. 1,624The critical values and the test characteristics of the group sequential test design were calculated for the O'Brien and Fleming design.

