2.3). The comparison will use the Cox-PH model. The tests are performed on a 5% level. In addition an explorative comparison of the event rates in the CEA and the CAS groups will be done (Calculating a 95% confidence interval of the hazard rate for the primary endpoint between both treatments). In order to analyze the effect between these two interventional methods, an indirect treatment comparison will be performed.

Trial Duration and Dates:

Follow-up per patient: 5 years

First patient in to last patient out: 8 years (3-year-recruiting phase, 5-year-follow-up)

Total trial duration 9 years

Duration of treatment per patient: Stent-protected angioplasty and carotid endarterectomy are performed within 4 weeks of randomization. Best medical treatment continues throughout the follow-up period.

ABBREVIATIONS

AE	Adverse Event
BDSG	Bundesdatenschutzgesetz
BMBF	Bundesministerium für Bildung und Forschung
BMT	Best medical treatment
CAS	Carotid artery stenting
CEA	Carotid endarterectomy
CRF	Case Report Form
CTCAE	Common Toxicity Criteria for Adverse Events
CV	Curriculum Vitae
DBL	Data Base Lock
DFG	Deutsche Forschungsgemeinschaft
DMC	Data Monitoring Committee
DVP	Data Validation Plan
EC	Ethics Committee
EEC	Endpoint Evaluation Committee
ExC	Executive Committee
ECG	Electrocardiogram
GCP	Good Clinical Practice
ICH	International Conference on Harmonization of Technical Requirements for Registration of Pharmaceuticals for Human Use
ISF	Investigator Site File
ISRCTN	International Standard Randomized Controlled Trial Number
ITT	Intention To Treat
KKS	Coordination Center for Clinical Trials (Koordinierungszentrum für Klinische Studien)
LKP	Coordinating Investigator according to German law (Leiter der Klinischen Prüfung)
n.a.	not applicable
OE	Outcome Event
SAE	Serious Adverse Event
SC	Steering Committee
SDV	Source Data Verification
SUSAR	Suspected Unexpected Serious Adverse Reaction
TMF	Trial Master File

TABLE OF CONTENTS

Clinical Trial Protocol Summary	2
Abbreviations	5
Table of Contents	6
Flow Chart / Trial Schedule	9
1 Introduction	12
1.1 Scientific background	12
1.1.1 Evidence	13
1.1.2 Role of conservative treatment	13
1.1.3 Role of carotid endarterectomy	13
1.1.4 Role of carotid artery stenting	14
1.2 Trial rationale/ justification	14
1.3 Benefit / risk assessment	15
2 Trial Objectives and Endpoints	16
2.1 General aim / primary objective	16
2.2 Assessment of safety	16
2.3 Composite primary efficacy endpoint	16
2.4 Secondary and tertiary outcomes	17

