1.1.1 Evidence

Asymptomatic carotid artery stenosis, per definition, can be found only in the context of screening examinations. Due to the lack of systematic screening examinations valid data about prevalence is not known. It is estimated that the prevalence of asymptomatic carotid artery stenoses $\geq 50\%$ is around 2-8%, and of stenoses $\geq 80\%$ around 1-2% [9]. Moderate to severe ($\geq 70\%$) asymptomatic stenosis of the extracranial carotid artery leads to an increased rate of stroke of approximately 11% in five years [8, 12]. Patients with asymptomatic carotid stenosis, however, are at also higher risk of non-stroke vascular events. The estimated annual risks of such events in patients with asymptomatic stenosis are 7% for coronary ischemic event and 4-7% for overall mortality [15].

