5.5 Follow-up examinations

The duration of the trial for each subject is 5 years. After the periprocedural phase yearly examinations are scheduled. Each visit consists of an event-screening, a risk-factor screening, and an ultrasound-examination.

The 30day visit for patients randomized into the BMT-arm is primarily used to evaluate if the recommendations for risk-factor-modification have been fulfilled.

Events are screened using a standardized questionnaire. An event has occurred if one of the following questions has been answered positively:

„Ist (seit der letzten Untersuchung) eine vorübergehende Sehstörung auf einem Auge aufgetreten?“

„Ist (seit der letzten Untersuchung) eine Schwäche oder Sensibilitätsstörung auf einer Körperseite aufgetreten?“

„Ist (seit der letzten Untersuchung) eine Sprachstörung aufgetreten?“

„Haben sich (seit der letzten Untersuchung) neue Beschwerden entwickelt?“

If a cerebrovascular outcome-event occurred an appropriate neuroimaging should be performed to distinct between possible types of stroke. In addition the mRS and NIHSS have to be assessed and documented. 30 days after symptom onset the patient has to be contacted to assess the mRS at this time point. In case of an ipsilateral cerebrovascular event in a subject randomized into the BMT-arm, patient should be considered for CEA or CAS following actual guidelines for treatment of symptomatic stenosis.

Risk-factor screening, assessment of medication, and ultrasound-examinations has to be done at any follow-up visit like described above (section 5.2)

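### Section 9.1 bases 1,636 patients on 5-year accrual plus 3-year follow-up run to year 8; with the 5 years per patient fixed elsewhere, power is about 76%, not 80%

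*Protocol*

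**What the plan says.** Protocol section 9.1 (NEW) sets the planning assumptions: "The event rate in the BMT-group is expected as 0.01 per year" and "a hazard ratio with any type of intervention is set as 0.50 leading to an average risk of 0.005 per year", tested "on a two- sided significance level of 5% and with a power of 80"%. Two totals follow.

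- Without an interim: 1,624 patients, "with a power of 80% assuming an accrual time of 3 years and a follow-up time of 5 years".
- With one interim after five years (O'Brien-Fleming): 1,636 patients, "with a power of 80% assuming an accrual time of 5 years and a follow-up time of 3 years". This is the adopted size, 818 per arm in each substudy (section 4.1).

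Other sections describe the follow-up differently from the second pair.

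- Summary, Trial Duration and Dates: "First patient in to last patient out: 8 years (3-year-recruiting phase, 5-year-follow-up"), with 5 years of follow-up per patient.
- Section 5.1: the last scheduled visit is at 5 years.
- Section 5.5: "The duration of the trial for each subject is 5 years".
- Sections 2.3, 6.3.1 and 9.2: the primary endpoint counts ipsilateral ischemic stroke up to 5 years. Death counts only within the first 30 days.

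Section 1.1.1 cites annual risks in patients with asymptomatic stenosis, including "4-7% for overall mortality". Section 9.1 (NEW) states no allowance for death or loss.

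**The concern.** The two totals are presented as the same trial without and with an interim, and they differ by only 12 patients. Yet the accrual and follow-up times are swapped between them. In a trial driven by event counts, that swap should change the number of patients considerably, so at least one label cannot belong to its number.

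The second question is which follow-up the adopted 1,636 assumes. If early entrants are counted for up to 8 years, the calculation uses person-time that the protocol neither schedules visits for nor counts in the endpoint. The 80% power is then not the power of the trial described. Each substudy expects only about 60 to 66 events, so losing five or six is visible in the power. The same pair also sets how much information is available at the five-year efficacy interim.

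**Working it through.** **Inputs.** Hazards 0.01 (BMT) and 0.005 (intervention) per year, two-sided 5%, power 80% (section 9.1); 1:1 allocation (section 4.1). Assumed: exponential event times, uniform entry, no losses unless stated.

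**Events needed (Schoenfeld).** 4 × (1.960 + 0.842)² / (ln 0.5)² = 65.35.

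**Event probability to study end**, with accrual A and minimum follow-up F: p = 1 − [exp(−λF) − exp(−λ(A+F))] / (λA).

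**Reproducing the plan's figures: 5 + 3, counted to year 8**
- λ = 0.01: p = 0.05342. λ = 0.005: p = 0.02710. Mean 0.04026.
- N = 65.35 / 0.04026 = 1,623.2, rounded up to 1,624.
- The two-look O'Brien-Fleming factor at half information is 1.0078. 1,623.2 × 1.0078 = 1,636.

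Both printed totals are recovered.

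**The pair printed beside 1,624: 3 + 5, counted to study end**
- p = 0.06290 and 0.03197, mean 0.04743. N = 65.35 / 0.04743 = 1,378.
- 1,624 patients would then have 77.0 events and 86% power.

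Freedman's formula (70.6 events) gives 1,489 for 3 + 5 to study end, 1,923 for a fixed 5 years and 1,755 for 5 + 3 to study end. None of these is a printed figure.

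**The trial described: 5 years for every patient**
- p = 1 − exp(−0.05) = 0.04877 and 1 − exp(−0.025) = 0.02469, mean 0.03673.
- Expected events with 1,636 patients: 1,636 × 0.03673 = 60.1.
- Power = Φ(½ × √60.1 × ln 2 − 1.960) = Φ(2.687 − 1.960) = 76.6%; with the interim at half information, 76.3%.
- N for 80%: 65.35 / 0.03673 ≈ 1,779 before rounding up, so about 1,780; with the interim at half information, 1,793.

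With a fixed 5 years per patient, the length of accrual does not affect final power. It does affect the interim.

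**Information at five calendar years from first patient in**
- 3 + 5, 5 years per patient: patients have 2 to 5 years of follow-up, mean 3.5 of 5, so the fraction is about 0.70.
- 5 + 3, run to study end: mean 2.5 of 5.5 years, about 0.46.
- At 0.70 the O'Brien-Fleming factor is 1.018. The effective events are 60.1 / 1.018 = 59.0, and power is still about 76%.

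**Sensitivity to mortality.** Treat death after day 30 as independent censoring at rate μ: p = λ/(λ+μ) × [1 − exp(−5(λ+μ))], with 1,636 patients.

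| μ per year | Expected events | Power, fixed | Power, with interim (half information) |
|---|---|---|---|
| 0 | 60.1 | 76.6% | 76.3% |
| 0.04 | 54.5 | 72.5% | 72.2% |
| 0.07 | 50.8 | 69.5% | 69.1% |

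**The case against.** **The wrong label sits on an unused number.** Section 9.1 attaches 3 + 5 only to 1,624, the design that was not adopted. A reader might infer that both totals are attributed to 3 + 5, but the text does not say so: 1,636 is printed with the pair that reproduces it. A stray 1,624 later in the same section suggests leftover editing. This stands, and the label alone is a clerical slip. It does not reconcile the basis of 1,636 with 5 years per patient.

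**Three plus five could mean more power.** Counted to study end, 1,636 patients would have 86%. But no visit is scheduled after year 5 and the endpoint stops there, so the documents rule this reading out. A loss of roughly 5% a year under that reading would also bring N near 1,624, but no such loss is stated and the 5-year limit would still be breached.

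**The gap is modest.** With 5 years per patient, 1,636 patients have 80% power for a hazard ratio of 0.483 instead of 0.50, or with a BMT rate of about 0.011 instead of 0.010. This stands as to size. The stated power is still not what the stated assumptions give.

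**Stronger readings the documents do not support**
- *That true power is about 70%.* The 4-7% is background mortality for asymptomatic stenosis in general, whereas section 4.4 excludes life expectancy below 5 years, a modified Rankin score above 1 and recent malignancy. Section 9.1 also does not say whether its rate is net of death.
- *That power falls to 66-73%.* This needs 5-year accrual, closure at year 8 and a 5-year cap together. Late entrants would then get less than the 5 years promised in the summary and section 5.5.
- *That equal allocated and analyzed numbers show an error.* Under intention to treat all allocated patients are analyzed, and section 4.5.1 censors withdrawals.

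**Conclusion.** The point holds in two parts. The 1,624 in section 9.1 carries the wrong accrual and follow-up pair. The adopted 1,636 rests on follow-up to year 8, which contradicts the 5 years per patient set in the summary, the visit plan, section 5.5 and the endpoint.

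For the trial as described, each substudy expects about 60 events and has about 76% power, some 4 points below the stated 80%. This rests on the protocol's own hazards, exponential event times, the Schoenfeld formula and no losses; it needs no mortality assumption. The 69-72% under 4-7% annual mortality is a sensitivity range that also assumes deaths are independent censoring and that the planning rate is net of death.

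**What to change.** In section 9.1:

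1. Use one accrual and follow-up pair for both designs, with 5 years per patient. The summary's 3-year recruitment and 5-year follow-up is the obvious candidate. If recruitment is now expected to take 5 years, the summary's 8 years from first patient in to last patient out must become 5 + 5 = 10.
2. Correct the 1,624 sentence and remove the stray repeat of that figure.
3. Restate the power of 1,636 per substudy as about 76%, with about 60 expected events.
4. Add power under the cited 4-7% annual mortality (about 69-72%), labelled as a sensitivity range with its censoring assumption.
5. Base the five-year interim in section 9.5 on the same pair and state the expected information fraction: about 0.70 under 3 + 5 with 5 years per patient, against about 0.46 under the present 5 + 3 basis.

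The cost is one rewritten paragraph, a consistency check of the summary and section 9.5, and a lower stated power. No extra patients are needed for this correction. If the sponsor prefers to keep 80%, the fixed design needs about 1,780 per substudy before any allowance for mortality, which is about 144 more than 1,636.

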9.2 Analysis variables

Safety is assessed as the rate any stroke within 30 days of treatment, and death from any cause within 30 days. The primary efficacy endpoint is the cumulative rate of any stroke or death from any cause within 30 days plus ipsilateral ischemic stroke within 5 years of follow up. Both safety and efficacy are also evaluated by analyzing secondary and tertiary endpoints as described in section 2 and 6.

9.3 Definition of trial population to be analyzed

The primary analysis will be intention-to-treat (ITT). In addition, due to the nature of a non-inferiority study, a per-protocol (PP) analysis will also be performed. The PP includes all patients without major protocol deviations. The following are considered major protocol deviations:

- Not meeting one or more of the Inclusion Criteria and/or falling into one or more of the Exclusion Criteria
- Not finishing the allocated therapy (change of treatment group)
- Operation or Stenting done by an non-certified interventionalist or using non-certified material
- Endpoint event between randomization and treatment (if allocated to CEA or CAS)

In case of problems with the decision if a protocol violation is major, the Endpoint Evaluation Committee (see page 40) is responsible for the allocation; this will be done prior the unblinding of the data.

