4.5 Criteria for withdrawal

4.5.1 Withdrawal of subjects

A subject may be withdrawn from all trial related procedures (including follow-up visits) for the following reasons:

at his/her own request or at request of his legal representative

non-adherence to the trial-related requirements, which may (have) influence(d) the validity of the trial data

If, in the investigator's opinion, continuation of the trial would be detrimental to the subject's well-being, e.g. if a patient was randomized into the BMT arm and suffers ipsilateral neurological symptoms, patient treatment based on actual guidelines either with CEA or CAS

Occurrence of exclusion criteria

If, in the investigator's opinion, protocol violations caused by the subject would lead to invalid data (e.g. non-compliance with planned study procedures).

The Executive Committee (see chapter 10.2) decides about withdrawal of subjects from trial treatment in case of occurrence of criteria mentioned above. A withdrawn patient will be treated as censored at time of leaving the study.

In all cases, the reason for withdrawal must be recorded in the CRF and in the subject's medical records. In case of withdrawal of a subject at his/ her own request, the reason should be asked for as extensively as possible and documented. All efforts will be made to follow up the subject and, all examinations scheduled for the final trial day will be performed as far as possible on all subjects and documented. All ongoing Adverse Events (AEs) / Serious Adverse Events (SAEs) of withdrawn subjects have to be followed up until no more signs and symptoms are verifiable or the subject is on stable condition.

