5.2 Screening and randomization

To qualify for this trial, patients must have met all above described inclusion and none of the exclusion criteria. Screening and randomization can be done at the same day, and randomization must be done within 14 days after screening, otherwise screening-examinations have to be repeated. The interventional therapy that will be tested vs. BMT has to be chosen by the treating physician and the patient prior to randomization. Following this decision patients will be assigned to SPACE2a or SPACE2b. Randomization between BMT and intervention is performed after the eligibility of a patient has been accepted by the involved discipline and after the patient has been examined from the study neurologist. Randomization will be done with an internet-based system provided by the data-center in Munich. Randomization will be stratified by an age-limit of 75years, providing the same numbers of instances per group in both age-cohorts. If the patient has been randomized to the interventional arm, treatment must be done within 4 weeks after randomization. Events occurring between randomization and treatment are counted within the allocated treatment group. Events between screening and randomization are not counted, but have to be noticed in preexisting condition in the CRF.

Before randomization following procedures has to be done:

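### Section 9.3 defines the per-protocol set partly by outcome: a pre-treatment endpoint event excludes CEA/CAS patients only, and BMT patients treated after an event could also be dropped

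*Protocol*

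**What the plan says.** Section 9.3, which is current text and not marked as superseded, states: "The primary analysis will be intention-to-treat (ITT"). It then adds a second analysis: "due to the nature of a non-inferiority study, a per-protocol (PP) analysis will also be performed". The PP set holds patients without major deviations. Two of the four listed deviations matter here:

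- "Endpoint event between randomization and treatment (if allocated to CEA or CAS"). There is no counterpart for BMT.
- "Not finishing the allocated therapy (change of treatment group"). No exception is made for a change that follows an endpoint event.

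Section 9.3 leaves doubtful cases to the Endpoint Evaluation Committee, before unblinding.

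Other sections bear on these two criteria:

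- Section 5.2: "Events occurring between randomization and treatment are counted within the allocated treatment group".
- Section 6.1 (observation period) starts the 30-day risk window for CEA and CAS at randomization, so it includes the wait for the procedure.
- Section 5.5, on a BMT patient with an ipsilateral cerebrovascular event: "patient should be considered for CEA or CAS following actual guidelines for treatment of symptomatic stenosis".
- Section 4.5.1 gives the same pathway as an example of a reason for withdrawal ("if a patient was randomized into the BMT arm and suffers ipsilateral neurological symptoms") and censors withdrawn patients when they leave the study.

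**The concern.** Membership of an analysis set should not depend on the outcome being analysed. The first criterion makes it do so in one arm. To enter the PP set, a CEA or CAS patient must survive event-free until the procedure, up to 28 days after randomization, while a BMT patient faces no such requirement. This is immortal time in the intervention arm, and it removes events that sections 5.2 and 6.1 say belong to that arm. The direction is fixed: it favours intervention.

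The second criterion could act the other way. Suppose CEA or CAS given after an ipsilateral event counts as a change of treatment group. Then a BMT patient who has an endpoint stroke and is managed along the path foreseen in sections 4.5.1 and 5.5 leaves the PP set, and the stroke leaves too. That favours BMT.

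What is at stake is how the PP result can be read beside ITT. If both criteria operate, agreement or disagreement between the two analyses says little, because the net direction depends on a crossover share that the protocol does not give.

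**Working it through.** **Inputs from the protocol.** BMT rate 0.01 per year, hazard ratio 0.50, intervention rate 0.005 per year, two-sided 5%, power 80%, accrual A = 5 years and follow-up F = 3 years (section 9.1, amended text); 818 patients per arm (section 4.1); at most 28 days to treatment (sections 5.1 and 5.3.1); overall mortality 4–7% per year (section 1.1.1).

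**Assumptions.** Constant hazards; uniform accrual; every intervention patient waits the full 28 days; an inflation factor of 1.0078 for a two-look O'Brien-Fleming design; illustrative removal of 10%, 25% or 50% of BMT events.

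**Step 1: reproduce the planned size.**
- Events needed (Schoenfeld): 4 × (1.960 + 0.842)² / (ln 0.50)² = 65.3.
- Event probability: P = 1 − exp(−λF) × (1 − exp(−λA)) / (λA). This gives 5.34% for BMT and 2.71% for intervention.
- Fixed-design N = 65.3 / ((0.0534 + 0.0271)/2) ≈ 1,623; × 1.0078 ≈ 1,636, the stated figure.
- Expected events per substudy: 818 × 5.34% ≈ 43.7 (BMT) and 818 × 2.71% ≈ 22.2 (intervention).
- Person-years: 43.7/0.01 ≈ 4,369 and 22.2/0.005 ≈ 4,434.

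**Step 2: pre-treatment exclusion (CEA/CAS only).** Events removed: x = 818 × (1 − exp(−r × 28/365.25)).
- r = 0.005: 0.3. r = 0.01: 0.6.
- r = 0.01 + 0.04: 3.1. r = 0.01 + 0.07: 5.0. These two are upper bounds.

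PP ratio: ((22.2 − x)/4,434) / 0.01. For x = 0.6, 3 and 5 this is 0.49, 0.43 and 0.39. The excluded patients' own person-time is at most 28 days each and is ignored.

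**Step 3: crossover exclusion, if the literal reading applies.** Let f be the share of BMT primary endpoint events removed. Each excluded patient is taken to lose half the mean follow-up, (5/2 + 3)/2 = 2.75 years. PP ratio: 0.005 / [43.7(1 − f) / (4,369 − 43.7 × f × 2.75)].
- f = 10%: 0.005/(39.3/4,357) = 0.55.
- f = 25%: 0.005/(32.8/4,339) = 0.66.
- f = 50%: 0.005/(21.8/4,309) = 0.99.

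**Step 4: both together, true ratio 0.50.**

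| Intervention events removed | f = 0 | 10% | 25% | 50% |
|---|---|---|---|---|
| 0 | 0.50 | 0.55 | 0.66 | 0.99 |
| 0.6 | 0.49 | 0.54 | 0.64 | 0.96 |
| 3 | 0.43 | 0.48 | 0.57 | 0.85 |
| 5 | 0.39 | 0.43 | 0.51 | 0.76 |

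With a true ratio of 1.0, step 2 alone gives 0.99, 0.93 and 0.89, and step 3 alone gives 1.11, 1.32 and 1.97. Following every patient for exactly five years (39.9 and 20.2 expected events) moves no entry in the table by more than about 0.02.

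**The case against.** The first criterion cannot be read away, but the rest can be challenged.

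- **The crossover reading is not explicit.** Section 5.5 says only that such patients be considered for CEA or CAS. Care that the protocol foresees is not obviously a deviation, and the bullet speaks of not finishing the allocated therapy. Under section 4.5.1 an endpoint stroke before withdrawal is still counted, because censoring comes later. All this stands: the text permits the exclusion but does not state it. Section 4.5.1, however, governs censoring, not membership of the PP set, so it does not settle the question.
- **The committee decides doubtful cases.** This helps only in part. Section 6.4 describes the committee as blinded to treatment, while both criteria depend on the allocation or on the treatment received.
- **The larger figures are fragile.** A reader might infer that 14% to 23% of intervention events are lost (3.1/22.2 to 5.0/22.2). That sets deaths at general background mortality against a count planned at 0.5% per year. It also has everyone wait 28 days, and section 4.4 excludes patients with a life expectancy under five years. A reader might also infer that PP would turn a ratio of 0.50 into no effect. That needs half of all BMT events to be removed, a share found nowhere in the protocol. The 43.7 events are also the whole composite: deaths and non-ipsilateral strokes within 30 days do not lead to the section 5.5 pathway. Both objections stand.
- **ITT is primary.** This stands. Nothing in the amended text makes a test or stopping rule depend on PP.
- **The non-inferiority wording is only a leftover.** Largely so. The protocol summary still carries an unmarked non-inferiority line for safety, but the amended section 9.4 uses stopping thresholds for safety and tests intervention against BMT for a difference in efficacy.

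**Conclusion.** The point holds for the PP analysis only. The exclusion of pre-treatment endpoint events is explicit, one-sided, at odds with sections 5.2 and 6.1, and favours intervention. Its size at the planning rates is slight, 0.50 to about 0.49; the 0.43 to 0.39 range is an upper bound resting on a 28-day wait for all 818 patients and 4–7% annual mortality plus 1%.

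The crossover exclusion is a plausible literal reading that section 9.3 should settle. If it applies it could well be the larger of the two, but its size is unknown; 0.55, 0.66 and 0.99 are illustrations for removal of 10%, 25% and 50% of BMT events. The documents do not support saying that the protocol requires this exclusion, or that the PP result will be null. Neither criterion touches the primary ITT result, which keeps all these events.

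**What to change.** Amend section 9.3 as follows:

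1. Delete the exclusion for an endpoint event between randomization and treatment, and count those events in the allocated arm, as section 5.2 already requires.
2. Limit the change-of-treatment-group criterion to changes made before any primary endpoint event. A BMT patient who has such an event and later receives CEA or CAS then stays in the PP set with the event counted.
3. Replace the non-inferiority justification with one that fits the two superiority comparisons, and label PP a sensitivity analysis to ITT.

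The cost is rewording. Fewer patients are excluded, the sample size is unchanged, and no treatment rule changes.
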